5. OBJECTIVES AND ENDPOINTS

The objectives and endpoints for both arms of this signal finding study are to evaluate the treatment with selinexor plus pembrolizumab are same as listed below:

Objectives	Endpoints
Primary	

• To evaluate objective response rate (ORR) per RECIST v1.1 response criteria.	
• ORR defined as the proportion of patients who achieved a complete response (CR) or a partial response (PR).
Secondary	
• To evaluate progression-free survival (PFS) per RECIST v1.1 response criteria.• To evaluate overall survival (OS).• To evaluate rates of CR.• To evaluate duration of response (DOR)• To evaluate the disease control rate (DCR) 
• PFS defined as time from date of first treatment to the date of first confirmed progressive disease (PD) or death due to any cause, whichever occurs first.• OS defined as time to death, from the date of first treatment.• Complete response rate (CRR), defined as proportion of patients who achieved a CR.• DOR defined as the duration of time from first occurrence of response \geqPR until the first date of PD or death due to any cause, whichever occurs first.• DCR is defined as the percentage of patients who have achieved CR, PR and stable disease (SD). 
• To evaluate the safety and tolerability of selinexor and pembrolizumab combination regimen. 
• Safety and tolerability of study treatment will be evaluated based on adverse event (AE) reports, vital signs, clinical laboratory results, and physical examination findings, by the occurrence, nature, and severity of AEs as categorized by the Common Terminology Criteria for Adverse Events (CTCAE) v5.0.

[figure not shown]
Objectives	Endpoints
Exploratory	CCl

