10.3.1.1. RECIST

Disease response will be assessed according to the RECIST criteria v1.1 ([Appendix 1](#)).

10.3.1.2. iRECIST

Antitumor response based on assessment of changes in tumor burden will be assessed by iRECIST ([Appendix 2](#)). The RECIST 1.1 definitions will be used to determine “immune” response: PFS and ORR.

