12.4.1.1. Primary Endpoint

The primary efficacy endpoint of ORR (proportion of patients who achieve CR or PR) will be analyzed for each arm separately on the mITT population which consists of all enrolled patients who received any study treatment. Estimated ORR with 95% confidence interval (CI) will be summarized for each arm.

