APPENDIX 1. RECIST VERSION 1.1

(Modified from [Eisenhauer 2009](#))

All patients will have their BEST RESPONSE on study classified as outlined below:

Complete Response (CR)

Disappearance of all target lesions. Any pathological lymph nodes (whether target or non target) must have reduction in the short axis to <10mm.

Partial Response (PR)

At least a 30% decrease in the sum of diameters of target lesions, taking as reference the baseline sum diameters.

Stable Disease (SD)

Steady state of disease. Neither sufficient shrinkage to qualify for PR nor sufficient increase to qualify for PD.

Progressive Disease (PD)

At least a 20% increase in the sum of diameters of measured lesions taking as references the smallest sum of diameters recorded since the treatment started. In addition to the relative increase of 20%, the sum must also demonstrate an absolute increase of at least 5 mm. Appearance of one or more new lesions will also constitute progressive disease.

Response Duration

Response duration will be measured from the time measurement criteria for CR/PR (whichever is first recorded) are first met until the first date that recurrent or progressive disease is objectively documented, taking as reference the smallest measurements recorded since the treatment started.

Stable Disease Duration

Stable disease duration will be measured from the time of start of therapy until the criteria for progression are met, taking as reference the smallest measurements recorded since the treatment started.

Evaluation of Best Overall Response – Patient with Target (\pm non-target) disease

Target lesions	Non-Target lesions	New Lesions	Overall response
CR	CR	No	CR
CR	Non-CR-Non-PD	No	PR
CR	NE	No	PR
PR	Non-PD/or not all evaluated	No	PR
SD	Non-PD/or not all evaluated	No	SD
Not all evaluated	Non-PD	No	NE

Target lesions	Non-Target lesions	New Lesions	Overall response
PD	Any	Yes or No	PD
Any	PD	Yes or No	PD
Any	Any	Yes	PD

CR: complete response; NE: non-evaluable; PD: progressive disease; PR: partial response; SD: stable disease.

Evaluation of Best Overall Response – Patient with Non-Target Disease

Non-Target lesions	New Lesions	Overall response
CR	No	CR
Non-CR-Non-PD	No	Non-CR/Non-PD ¹
Not all evaluated	No	NE
Unequivocal PD	Yes or No	PD
Any	Yes	PD

CR: complete response; NE: non-evaluable; PD: progressive disease; PR: partial response.

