Immune best overall response (iBOR) is determined as with RECIST 1.1 if there is no iUPD. In the case of iUPD, a subsequent iBOR of iSD, iPR, or iCR is still possible if the overall RECIST 1.1 criteria are met, provided that the criteria for iCPD (that is, disease progression at the assessment following iUPD) are not met. The duration of iCR and iPR is from the timepoint when criteria for iCR or iPR are first met; the duration of iSD is calculated from baseline.

For immune progression-free survival (iPFS), the event date should be the first date at which progression criteria are met (ie, the date of iUPD) provided that iCPD is confirmed at the next assessment. The date of an iUPD that is disregarded due to iSD, iPR, or iCR at the next visit should not be used as the progression event date. [Table 13](#) illustrates comparisons between RECIST 1.1 and iRECIST, and [Table 14](#) provides guidance for assigning timepoint response without or with previous iUPD.

Comparison of RECIST 1.1 and iRECIST

	RECIST 1.1	iRECIST
Definitions of measurable and non-measurable disease; numbers and site of target disease	Measurable lesions are ≥ 10 mm in diameter (≥ 15 mm for nodal lesions); maximum of 5 lesions (2 per organ); all other disease is considered non-target (must be ≥ 10 mm in short axis for nodal disease)	No change from RECIST 1.1; however, new lesions are assessed as per RECIST 1.1 but are recorded separately on the eCRF (but not included in the sum of lesions for target lesions identified at baseline)
Complete response, partial response, or stable disease	Cannot have met criteria for progression before complete response, partial response, or stable disease	Can have had iUPD (one or more instances), but not iCPD, before iCR, iPR, or iSD
Confirmation of complete response or partial response	Required for non-randomized trials	As per RECIST 1.1
Confirmation of stable disease	Not required	As per RECIST 1.1
New lesions	Result in progression; recorded but not measured	Result in iUPD, but iCPD is assigned on the basis of this category ONLY if at the next assessment additional new lesions appear or an increase in size of new lesions is seen (≥ 5 mm for sum of new lesion target or any increase in new lesion non-target); the appearance of new lesions when none have previously been recorded, can also confirm iCPD.
Confirmation of progression	Not required	Required

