1.3.1. Primary Endpoint

 ORR, defined as proportion of patients who achieved a CR or partial response (PR) per RECIST v1.1

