4.2. Primary Efficacy Endpoints

4.2.1. ORR

ORR is defined as the proportion of patients who achieve CR or PR per RECIST v1.1.

The primary efficacy endpoint of ORR will be analyzed for each arm separately on the mITT population which consists of all enrolled patients who received any study treatment. Estimated ORR with 95% exact confidence interval (CI) will be summarized for each arm.

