4.3. Secondary Efficacy Endpoints

4.3.1. Definition of Secondary Efficacy Endpoints

Table 4-1 are the secondary efficacy endpoints:

Table 4-1 Efficacy Endpoints and Definitions

Endpoint	Definition
Secondary Endpoints	
Progression-free survival (PFS)	Duration of time from date of first study treatment until the first date that PD assessed by RECIST 1.1 is objectively documented or death due to any cause. Refer to Table 4-2 for details on PFS outcome status (PFS event vs. censored) and censoring definitions.
Overall survival (OS)	Duration from the date of first study treatment until death due to any cause. If death event did not occur during the follow-up period, the patient is censored at the date of discontinuation from the study (i.e. withdrawal of consent), or date of last participating visit (e.g., a telephone contact with patient status being alive) on or before database cutoff date, whichever occurs first.
Complete response rate (CRR)	Proportion of patients who achieved a CR per RECIST 1.1
Duration of response (DOR)	Duration of time from first meeting CR or PR measurement criteria (whichever occurs first) until the first date that PD recurrence is objectively

	documented or death due to any cause. Responses are assessed per RECIST 1.1.
	Refer to Table 4-2 or details on the outcome and censoring definitions.
Disease control rate (DCR)	Proportion of patients who have a response of CR, PR, or SD ≥ 12 weeks. Responses are assessed per RECIST 1.1.

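### The documents disagree on whether the primary ORR needs confirmed responses, and they give no working confirmation rule

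*SAP*

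**What the plan says.** **Endpoint definitions.** The primary objective in Protocol 5 is "To evaluate objective response rate (ORR) per RECIST v1.1 response criteria". Protocol 12.4.1.1 reads: "The primary efficacy endpoint of ORR (proportion of patients who achieve CR or PR) will be analyzed for each arm separately". SAP 1.3.1 has "ORR, defined as proportion of patients who achieved a CR or partial response (PR) per RECIST v1.1", and SAP 4.2.1 repeats it: "ORR is defined as the proportion of patients who achieve CR or PR per RECIST v1.1". For CRR, SAP Table 4-1 has "Proportion of patients who achieved a CR per RECIST 1.1"; Protocol 12.4.1.2 and SAP 1.3.2 are equivalent. None of these mentions confirmation.

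**Response criteria.** Protocol 10.3.1.1 says "Disease response will be assessed according to the RECIST criteria v1.1" and refers to Appendix 1. That appendix is headed as a modification of the published criteria and opens with "All patients will have their BEST RESPONSE on study classified as outlined below". What follows is measurement thresholds and best-overall-response tables. It asks for no second scan to confirm a CR or PR and sets no interval between scans.

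**The one express statement.** Appendix 2 has a table comparing RECIST 1.1 with iRECIST. In the row on confirming CR or PR, the RECIST 1.1 column says "Required for non-randomized trials", and the iRECIST column defers to it.

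**Design.** Protocol 6.1 assigns 20 patients with primary resistance to Arm A and 20 with acquired resistance to Arm B, all on one regimen, with response assessed by the investigator. Protocol 10.3.1 schedules scans every 9 weeks for 6 months and every 3 months after that.

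**The concern.** The text that a programmer would follow for RECIST (Appendix 1) and the text that states what RECIST 1.1 requires (Appendix 2) lead to different primary endpoints. Under Appendix 1 read literally, a PR seen once and gone at the next scan makes the patient a responder. Under Appendix 2 it does not.

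This matters because the endpoint is investigator-read, the study is open-label and the arms are small. If the rule is left open, the choice between the two derivations could be made after the responses are known. Two programmers could also produce different ORRs from the same data, each citing the protocol.

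**Working it through.** **1. Does the Appendix 2 condition apply?** Arm is determined by type of resistance to prior therapy, both arms receive the same regimen, and no random allocation is described. The trial is therefore non-randomized. The mention of randomization in footnote c of Table 1 and of a randomization number in Protocol 8.2.1 appear to be left-over wording.

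**2. The two readings applied to one patient.** Take a PR at the week 9 scan and measurements at week 18 that meet neither PR nor PD.

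- *Appendix 1 alone:* the week 9 scan meets the PR threshold, so best response is PR and the patient is a responder.
- *Appendix 1 with Appendix 2:* the PR is not confirmed, so the patient is not a responder.

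Now suppose instead that there is no scan after week 9. The first reading again gives a responder. The second gives no answer, because no visible text says how a response without a later scan is classed.

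**3. Direction.** Let R be the number of patients in an arm with at least one CR or PR, and u the number of these never confirmed. Then unconfirmed ORR − confirmed ORR = R/20 − (R − u)/20 = u/20 ≥ 0. The difference cannot be negative.

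**4. Size per patient.** With u = 1, 1/20 = 5 percentage points.

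**5. Intervals.** SAP 4.2.1 specifies exact 95% limits. To check the method on a figure in the documents: Protocol 4.2 cites 21.4% (13.9, 30.5) in 103 patients. The count that gives 21.4% is 22, and Clopper-Pearson limits for 22/103 are 13.9% to 30.5%, as cited. The same method at n = 20 gives:

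| Responders | ORR | Exact 95% CI |
|---|---|---|
| 3/20 | 15% | 3.2 to 37.9 |
| 4/20 | 20% | 5.7 to 43.7 |
| 5/20 | 25% | 8.7 to 49.1 |
| 6/20 | 30% | 11.9 to 54.3 |

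In this range one reclassified patient moves the lower limit by 2.5 to 3.2 points. The table starts at 3 and stops at 6 because the two rates that the protocol cites for patients resistant to checkpoint inhibitors correspond to 0.214 × 20 = 4.3 and 0.31 × 20 = 6.2 responders. They are used here only to show that few responders are in play.

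**6. Can the scheduled scans confirm a response?** The only confirmatory-scan interval in the protocol is at least 4 weeks (Protocol 4.2, for progression at entry). Scans 9 weeks or 3 months (about 13 weeks) apart both exceed it. Patients who stop treatment without progression remain under 3-monthly disease assessment until progression, new therapy or withdrawal (Table 1 footnote b; Protocol 6.2 is similar). A later scan is therefore normally planned.

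**The case against.** The best answer is that the rule is already there by reference. The SAP defines ORR per RECIST v1.1, SAP 1.1 ties that name to the published criteria rather than to Appendix 1, and Appendix 2 says that those criteria require confirmation in a design like this one. Silence in Appendix 1 is not a statement that confirmation is unnecessary. This stands in part: a reader might infer that unconfirmed responses will be counted, and the documents do not show that. It does not close the point. Protocol 10.3.1.1 directs the reader to Appendix 1, which is a modified text, and even an imported rule has no interval and no class for a response without a later scan.

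Second, SAP 1.4, the protocol's sample-size section and the exploratory material are not public and could hold a response definition. That stands, and it limits confidence. It also rules out the inference that the two-stage decision in SAP 1.5 is affected, since its rates and cut-offs cannot be seen.

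Two further readings are tempting and should not be made.

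- *That two single-scan responders would carry an arm from the 21.4% benchmark to the 31% one.* The documents never set these rates against each other. They come from a different drug combination and from 13 patients on a different schedule. If 31% is 4/13, its exact 95% CI is 9.1 to 61.4, which contains the whole of 13.9 to 30.5.
- *That the conflicting end-of-treatment imaging conditions remove the confirming scan.* The synopsis requires a scan if the previous one was more than 3 weeks before, and Protocol 10.3.1 if it was more than 6 weeks old. The conflict is real. Because 3-monthly assessment continues, it affects confirmation only for patients who start new therapy, die or withdraw before the next scan.

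**Conclusion.** The point holds as an inconsistency and an under-specified rule for the primary endpoint. Appendix 1 and every visible ORR and CRR definition omit confirmation, Appendix 2 says it is required, and nothing visible makes it operational. The size is 5 percentage points per affected patient in an arm of 20, always towards a higher ORR when unconfirmed responses are counted. The documents do not say how many responses would fail confirmation, so no expected bias is given.

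The conclusion rests on three things: that the trial is non-randomized (inferred from how arms are defined), that each arm reaches the planned 20, and that no rule sits in the non-public sections. Confidence is moderate for the last reason. It should be fixed before responses are analysed.

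**What to change.** In SAP 4.2.1 and Table 4-1:

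- Define primary ORR and CRR on CR or PR confirmed at a later assessment, with a stated minimum interval, for example at least 4 weeks.
- Count a response with no confirming scan before new anti-cancer therapy as a non-response, keeping the patient in the mITT denominator. State how such a response is classed for DCR.
- Start DOR at the first scan of a confirmed response.
- Report unconfirmed ORR as supportive.

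Before using the rule at the interim, check that it matches the response definition behind the rates and cut-offs in SAP 1.4. Align Appendix 1 with Appendix 2 at the next protocol amendment.

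**Cost.** One derivation rule and a few lines in the SAP, which Protocol 12 allows to carry analysis changes. No scans beyond those scheduled are needed. The Appendix 1 text needs IRB/IEC approval under Protocol 13.1.1 and can wait for an amendment made for other reasons. ORR may be slightly lower, a read may wait one scan interval (9 weeks in the first 6 months, 3 months after that), and a response first seen at a patient's last scan counts only in the supportive analysis.

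**Side notes, not part of the ORR point.** The two end-of-treatment imaging conditions (Protocol 3.1 and 10.3.1) must be reconciled. So must the PFS wording: Protocol 12.4.1.2 dates progression from confirmed PD, SAP 1.3.2 and Table 4-1 from documented PD, and SAP 1.6 lists no modification.

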4.3. Secondary Efficacy Endpoints

4.3.1. Definition of Secondary Efficacy Endpoints

Table 4-1 are the secondary efficacy endpoints:

Table 4-1 Efficacy Endpoints and Definitions

Endpoint	Definition
Secondary Endpoints	
Progression-free survival (PFS)	Duration of time from date of first study treatment until the first date that PD assessed by RECIST 1.1 is objectively documented or death due to any cause. Refer to Table 4-2 for details on PFS outcome status (PFS event vs. censored) and censoring definitions.
Overall survival (OS)	Duration from the date of first study treatment until death due to any cause. If death event did not occur during the follow-up period, the patient is censored at the date of discontinuation from the study (i.e. withdrawal of consent), or date of last participating visit (e.g., a telephone contact with patient status being alive) on or before database cutoff date, whichever occurs first.
Complete response rate (CRR)	Proportion of patients who achieved a CR per RECIST 1.1
Duration of response (DOR)	Duration of time from first meeting CR or PR measurement criteria (whichever occurs first) until the first date that PD recurrence is objectively

	documented or death due to any cause. Responses are assessed per RECIST 1.1.
	Refer to Table 4-2 or details on the outcome and censoring definitions.
Disease control rate (DCR)	Proportion of patients who have a response of CR, PR, or SD ≥ 12 weeks. Responses are assessed per RECIST 1.1.

4.3.2. Analyses of Secondary Efficacy Endpoints

Analysis of secondary efficacy endpoints will be performed on the mITT population, unless otherwise stated.

4.3.2.1. Analyses of Binary Secondary Endpoints

Binary secondary endpoints of CRR and DCR will be calculated by point estimate with a 95% exact confidence interval (CI) using the exact method.

4.3.2.2. Analyses of Time to Event Secondary Endpoints

[figure not shown]
For each time to event secondary endpoint (PFS, OS and DOR), the number of patients with events, number of patients censored, estimates and 95% CI for the median of event time will be presented by treatment group.

[figure not shown]
Time-to-event will be plotted for each treatment group using the Kaplan-Meier method. The plot will include the number of patients at risk for each treatment group over time.

Table 4-2 PFS and DOR Outcome and Censoring Definitions

#	Situation	Date of event or censoring	Outcome
1	No baseline disease assessment	Date of first treatment	Censored
2	No adequate post-baseline disease status assessment unless death occurs prior to first post-baseline assessment	Date of first treatment	Censored
3	Documented PD without missing 2 or more consecutive assessments	Date of PD	Event
4	Death before documented PD and without missing 2 or more consecutive assessments	Date of death	Event
5	 No documented PD or death on or before Database cut Withdrawal of informed consent Lost to follow-up Date of discontinuation from treatment + 30 days Two or more consecutive missing assessments and the disease assessment result after the gap is PD¹ Start of new antineoplastic therapy, whichever occurs first 	Date of last adequate disease assessment prior to the events listed in the left column	Censored

^{1.} If disease assessment results after 2 or more consecutive missing assessments were not PD, the disease assessment gap will be ignored.

